#### ***Decision-making algorithm for initiating new dosing cohorts***

The study will be monitored by a DSMB, which will review the safety data for each cohort and will give approval before initiation of each possible dose escalation. Specifically, study drug dose will not be escalated and the study if any three participants develop grade 3 or higher musculoskeletal/CK-related adverse events (AEs), LFT-related AEs ( $> 5 \times UNL$  without symptoms, but  $> 3 \times UNL$  with symptoms or bilirubin  $> 2 \times ULN$ ) or any type of grade 4 event regardless of causal attribution. Study drug dosage will be escalated only if the dose is deemed safe/tolerable based on the above rules and the mean pravastatin AUC is reduced by  $\geq 40\%$  relative to the pre-Rifafour value. Study participants in whom the study drug has been discontinued will remain in the study until the final clinical visit and laboratory evaluation. In the event of study product discontinuation, management of the standard-of-care TB drugs will revert to the site clinician as per national guidelines.

#### ***Early stopping rules***

Early stopping of the study will be considered if adverse events occur in a great proportion or with greater severity than would be expected at the dosage of the study drug being used based on the safety profile in patients with cardiovascular disease. Upon reviewing the AE data, the DSMB will make a formal determination about early stopping of the study.

### ***Recruitment strategy***

Eligible patients (who meet all of the inclusion criteria and none of the exclusion criteria) will be recruited in a step-wise fashion to the study arms.

Although rifampin is known to reduce pravastatin plasma levels by 30-50% in healthy volunteers, the PK of pravastatin has not been studied during co-administration with the combination regimen Rifafour in patients with TB. Therefore, out of caution, we will begin to study pravastatin dosed at half the highest clinically recommended dose of pravastatin (40 mg/day). Drug exposures are expected to be lower following standard-of-care TB treatment (Rifafour) in the experimental group receiving pravastatin relative to pre-Rifafour pravastatin exposures.

Participants meeting entry criteria will be recruited sequentially into each study arm for 10 -30 evaluable participants.

This will be an open-label trial in which neither the participants nor the study staff will be blinded as to treatment assignment.

### **19. Risks**

#### ***Institutional Review Board Involvement***

This research will be conducted in compliance with the requirements of the US DHHS regulations to protect human subjects from research risk (45 CFR Part 46), in compliance with South African regulations protecting human subjects, and with oversight by the IRBs of Johns Hopkins University School of Medicine (FWA #00005752) and the University of Witwatersrand (FWA #00000715). All study personnel will complete a course in protection of human subjects prior to participating in the study.

The Investigator will ensure that the purpose of the study is explained to the participant and that written consent is obtained prior to participation in the study. The participant, Investigator or designee, and others as required by local regulatory guidelines will sign the consent prior to entry into the study. The participant will receive a copy of his/her signed consent form. The Investigator will retain a copy of the signed consent forms, which may be inspected at the monitor's or auditor's request.

The investigator will promptly report to the Ethics Committee/IRB and regulatory body of all changes in the research activity and all unanticipated problems involving risks to human subjects or others, and will not make changes in the research without Ethics Committee/IRB and regulatory body approval, except where necessary to eliminate apparent immediate hazards to human subjects.

Written informed consent will be obtained by trained study personnel prior to screening for inclusion and exclusion criteria. Informed consent is a process that will be initiated prior to the individual's agreeing to participate in the study and will continue throughout the individual's study participation.

#### ***Medical risks, listing all procedures, their major and minor risks and expected frequency.***

Risks associated with blood specimen collection include those related to venipuncture and blood loss. The risks of drawing blood from a vein include discomfort at the site of puncture; possible bruising and swelling around the puncture site; rarely an infection; and, uncommonly, faintness from the procedure.

### ***Steps taken to minimize the risks***

Appropriate clinical practices will be performed by trained clinical and study staff to minimize complications from the risk mentioned above.

### ***Plan for reporting unanticipated problems or study deviations.***

The Investigator will promptly report to the Ethics Committee/IRB and regulatory body of all changes in the research activity and all unanticipated problems involving risks to human subjects or others, and will not make changes in the research without Ethics Committee/IRB and regulatory body approval, except where necessary to eliminate apparent immediate hazards to human subjects.

### ***Legal risks such as the risks that would be associated with breach of confidentiality.***

Risks to confidentiality will be minimized by the following procedures: study records will be stored in locked cabinets in secure locations, study records will be accessible only by authorized study staff, and databases will be password-protected and accessible only to authorized study staff. Participant names will not be stored in the study database. All electronic communications involving study data will be encrypted. Laboratory results will be maintained in a password-protected file accessible only to study personnel. The study monitor(s) or other authorized representatives of the Sponsor may inspect all documents and records required to be maintained by the investigator.

### ***Financial risks to the participants.***

There are no financial risks to the participants. Treatment for TB is routine and free in South Africa. Participants will receive reimbursement for study visits in accordance with SAHPRA guidelines. There will be no other costs to the participants.

## **20. Benefits**

The proposed research may not have direct benefit to individual study participants. The South African government provides HIV medicines, TB medicines, and prenatal care to its citizens free of charge. For individuals in this trial, follow-up visits and counseling may enhance these services. In addition, study-related tests, such as viral load and resistance testing, may provide information regarding appropriate treatment that may benefit study participants directly. A better knowledge of the impact of statin adjunctive therapy for pulmonary TB is anticipated to inform public health practices and individual health activities to better treat drug-susceptible TB in HIV-infected and HIV-uninfected individuals. This will be especially pertinent in South Africa, a country that bears a disproportionate burden of HIV/TB co-infection.

## **21. Payment and Re-numeration**

Participants will receive reimbursement in line with South African guidelines and approved by the local Ethics Committee or SAHPRA.

## **22. Costs**

There are no costs to the participants.

Sputum AFB Smear and Culture In Liquid/Solid Media  (with DST)	x	x							x								x				
PK Sampling (intensive)		X 	X 														X 				
Urine pregnancy test	x																x		x		
Chest X-ray	x																				
CBC	x																				
DOT		X 	X 	x	x	x	x	x	x	x	x	x	x	x	x	x					
Lung Inflammation Assessment 		x														x		x			

Liver function tests (AST/ALT, T. bilirubin)

Chemistry (Comprehensive metabolic panel, total cholesterol, LDL, C-reactive protein, uric acid)

Two sputum samples for AFB smear microscopy and culture in liquid and solid media will be collected at each time point; sputum specimens and culture isolates will be stored

for culture-based drug-susceptibility testing and targeted deep sequencing in the event of TB treatment failure or TB recurrence.

 PK (intensive sampling)

 DOT of statin only

 DOT of statin and first dose of TB treatment

 Pulmonary function test, St George's Respiratory Questionnaire, 6-minute walk test; +/- 3 days

 Sparse PK

 The Screening evaluation process itself may occur over a few days; all Screening evaluations will be obtained within 3 days of study entry.

 Viral hepatitis serologies; IgM antibody for Hepatitis B surface antigen, IgM antibody to Hepatitis B core antigen, antibody to Hepatitis C

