##### ***Screening***

Participants with a presumptive diagnosis of sputum GeneXpert positive pulmonary TB will be invited to participate. Because culture confirmation is rarely available when TB treatment is initiated, patients will be recruited based on having a sputum specimen that is positive for TB by GeneXpert MTB/RIF.

Informed written consent, using IRB-approved consent forms, will be obtained by trained study personnel prior to performing any study-specific procedures. Informed consent is a process that will be initiated prior to the individual's agreeing to participate in the study and will continue throughout the individual's study participation.

The following will be performed after obtaining written informed consent:

- Eligibility criteria will be confirmed
- All participants will undergo HIV testing and counseling regardless of whether they have had a previous HIV test or not. HIV testing will be carried out with two rapid tests (the second test will be to confirm the result of the first); only one test need be carried out if the participant is known to have HIV, the single test will be confirmatory. Should there be a discrepancy between the two rapid tests, blood will be sent to the laboratory for enzyme-linked immunosorbent assay ELISA and Western Blot test in order to confirm the diagnosis.
- For HIV-positive participants, a CD4 count should be performed unless written results are available from a test done within the preceding 3 months or less.
- Participants will be asked questions related to demographics, current and past medical history, concomitant medications, alcohol and drug use and TB symptoms.
- Participants will have heart rate, blood pressure, respiratory rate, temperature and weight measured.
- An expectorated sputum sample will be obtained for GeneXpert MTB/RIF (as per inclusion criterion d), smear, culture, and drug susceptibility testing at the study laboratory (or documentation of results).
- Blood will be drawn for liver function tests (AST, ALT, total bilirubin), Hepatitis B and C serology, CK, serum creatinine, CBC (WBC, hemoglobin, and platelets).
- A posterior anterior chest radiograph will also be taken, unless a posterior anterior chest radiograph done within the previous 14 days or less is available for review.
- Urine will be collected for pregnancy testing if a woman is of child-bearing potential.
- Complete physical exam and vital signs
- 
- Targeted symptom assessment

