### ***Clinical Management of Adverse Events***

#### Liver toxicity

Study treatment will be permanently discontinued if any of the following criteria are met:

- ALT > 5x the upper limit of normal (ULN) without symptoms
- ALT > 3x ULN with signs or symptoms suggestive of clinical hepatitis including one or more of the following: nausea, vomiting, abdominal pain, dark colored urine or clay colored stools, unexplained fever, jaundice, liver tenderness, or hepatomegaly
- ALT > 3x ULN and Total Bilirubin  $\geq$  2x ULN

If a patient develops hepatic toxicity meeting the above stopping criteria, the following evaluation will be undertaken: assessment for history of injection or non-injection drug use, alcohol ingestion, use of other hepatotoxic drugs, and performance of serologic tests for viral hepatitis (IgM antibody for Hepatitis A, Hepatitis B surface antigen, IgM antibody to Hepatitis B core antigen, antibody to Hepatitis C). In addition, an AST and INR should also be checked, if not already done.

Participants will be followed until resolution (return to baseline) or stabilization of the ALT elevation.

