### ***Exclusion criteria:***

- a) A history of severe adverse reactions to any statin or any other study agent or contraindications to use of statins.
- b) Current use of statins or other lipid-lower agents;
- c) Clinical indication for statin therapy based on cardiovascular risk:
  - 1) Familial hypercholesterolemia
  - 2) Previous history of myocardial infarction or stroke
- d) For HIV-positive individuals, a CD4+ T-cell count <350/mm^3
- e) Use of antiretroviral drugs
- f) Hemoglobin concentration less than 8 g/dL;
- g) Baseline creatinine kinase elevation more than three times the upper limit of normal
- h) Abnormal baseline laboratory values
  - 1) Baseline alanine aminotransferase (ALT) concentration more than 2.5 times the upper limit of normal (Grade 1)
  - 2) Serum creatinine concentration more than twice the upper limit of normal;
  - 3) Serum total bilirubin level greater than twice the upper limit of normal
  - 4) Platelet count < 100,000/mm^3
  - 5) ANC <1,000/mm^3
- i) Pregnant or breastfeeding;
- j) Silico-tuberculosis.
- k) Currently receiving TB treatment
- l) Serologies or PCR positive for viral hepatitis (Hepatitis, B, C)
- m) Concomitant disorders or conditions for which isoniazid, rifampin, pyrazinamide, or ethambutol is contraindicated. These include cirrhosis, acute liver disease of any cause, acute uncontrolled gouty arthritis and peripheral neuropathy.
- n) Any medical or psychological condition which, in the view of the study investigator, makes study participation inadvisable.
- o) Infection with an isolate determined to be resistant to rifampin by GeneXpert.
- p) More than five days of anti-tuberculosis treatment within the previous 3 months
- q) Planned or current use of cyclosporine, tacrolimus, erythromycin or colchicine
- r) CNS TB
- s) Extra-pulmonary TB only, not in combination with pulmonary TB
- t) History of TB

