### ***Decision-making algorithm for pravastatin safety/PK study:***

Scenario/Pravastatin Dose	Safe/tolerable?	<math>AUC_{0-24}</math> reduction	Decision
1 40 mg daily	Y	=	Increase dose to prava 80 mg and enroll additional participants
2 40 mg daily	N	=	Enroll 5 additional participants (10 total) and discontinue study

3 80 mg daily	N	=	Discontinue study
4 80 mg daily	Y	< 40%	Discontinue study
5 80 mg daily	Y	≥ 40%	Increase dose to prava 120 mg and enroll additional participants
6 120 mg daily	N	=	Discontinue study
7 120 mg daily	Y	<40%	Discontinue study
8 120 mg daily	Y	≥ 40%	Increase dose to prava 160 mg and enroll additional participants
9 160 mg daily	N	=	Discontinue study
10 160 mg daily	Y	=	Study complete

Safety/tolerability: Y= Yes; <3 participants with  $\geq$  one grade 3 (or higher) event of musculoskeletal symptoms, creatine kinase elevation, or liver function test elevation attributed to study drug (probable or definite)

N= No; For Arm 1 (pravastatin 40 mg daily):  $\geq$  1 participant with  $\geq$  one grade 3 (or higher) event of musculoskeletal symptoms, creatine kinase elevation, or liver function test elevation attributed to study statin medication (probable or definite).

For Arms 2, 3, and 4:  $\geq$  3 participants with  $\geq$  one grade 3 (or higher) event of musculoskeletal symptoms, creatine kinase elevation, or liver function test elevation attributed to study statin medication (probable or definite)

$AUC_{0-24}$ = Area-under-the-plasma-concentration-time curve for 24-hour exposure

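### The only itemised screening hepatitis panel (Appendix 1, footnote 10) does not list hepatitis B surface antigen, unlike the Liver toxicity work-up, so screening as scheduled may miss chronic hepatitis B

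*Combined protocol and SAP*

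**What the plan says.** Four places bear on hepatitis testing.

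- **Section 4, Screening**, orders the blood draw in general terms: "Blood will be drawn for liver function tests (AST, ALT, total bilirubin), Hepatitis B and C serology, CK, serum creatinine". It names no hepatitis B marker.
- **Appendix 1, footnote 10**, itemises the panel, which the schedule marks at screening only: "Viral hepatitis serologies; IgM antibody for Hepatitis B surface antigen, IgM antibody to Hepatitis B core antigen, antibody to Hepatitis C".
- **Section 11, exclusion l**, excludes on "Serologies or PCR positive for viral hepatitis (Hepatitis, B, C". It names no marker. It allows PCR, but neither the Screening section nor Appendix 1 schedules one.
- **Section 5, Liver toxicity**, lists the serology to be done once a participant meets the liver stopping criteria: "IgM antibody for Hepatitis A, Hepatitis B surface antigen, IgM antibody to Hepatitis B core antigen, antibody to Hepatitis C".

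Liver events feed the dose decisions in three parts of Section 18.

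- **Decision-making algorithm for the safety/PK study:** Arm 1 fails if one participant, and Arms 2 to 4 fail if three participants, have a grade 3 or higher "event of musculoskeletal symptoms, creatine kinase elevation, or liver function test elevation attributed to study statin medication (probable or definite").
- **Data Analysis:** a regimen is safe only if nobody has to stop treatment for a pravastatin-related reaction, along with a limit on grade 3 events.
- **Decision-making algorithm for new dosing cohorts:** three participants with musculoskeletal/CK or liver events block escalation, "or any type of grade 4 event regardless of causal attribution".

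**The concern.** The Liver toxicity list and footnote 10 are almost the same string, but they name different tests. In the Liver toxicity list, the IgM wording applies to hepatitis A, and surface antigen follows as a separate item. In footnote 10 the IgM wording applies to surface antigen itself, so an antigen test has become an antibody test.

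A site that follows the schedule literally would then have no marker of established hepatitis B infection with which to apply exclusion l. Two things are at stake. The sponsor's own exclusion might not be delivered in a trial that adds pravastatin to three drugs with known liver effects. And a liver flare caused by undetected hepatitis B could be counted in small cohorts where very few events decide whether the dose goes up.

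**Working it through.** The plan states no figure that depends on this point, so there is nothing to reproduce. The check is a comparison of the texts, followed by an illustration of scale.

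**1. Side by side**

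| Place | Hepatitis B markers named | When it applies |
|---|---|---|
| Screening (Section 4) | none | screening |
| Appendix 1, footnote 10 | IgM antibody to surface antigen; IgM anti-core | screening only |
| Exclusion l (Section 11) | none; serology or PCR | eligibility |
| Liver toxicity (Section 5) | surface antigen; IgM anti-core | after stopping criteria are met |

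Removing *A, Hepatitis* from the Liver toxicity list gives footnote 10's list exactly. A transcription slip is the likeliest explanation.

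**2. What the literal panel detects.** This step rests on general knowledge of the markers, not on the documents. A chronic carrier has surface antigen, lacks antibody to it, and is usually negative for IgM anti-core because that marks recent infection. Such a person would be negative on both hepatitis B items in footnote 10.

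**3. What else would stop a carrier.** Exclusion h removes "Baseline alanine aminotransferase (ALT) concentration more than 2.5 times the upper limit of normal" and bilirubin above twice ULN. Exclusion m covers liver conditions ("These include cirrhosis, acute liver disease of any cause, acute uncontrolled gouty arthritis and peripheral neuropathy"). Exclusion n leaves room for investigator judgement. A carrier with normal or mildly raised ALT and no known liver disease passes h and m.

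**4. Scale, on assumed values only.** The documents give no carriage rate, so take p = 1%, 3%, 5% and 10%, and suppose that no carrier is screened out by any route. Then P(at least one carrier) = 1 − (1 − p)^n:

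| n | 1% | 3% | 5% | 10% |
|---|---|---|---|---|
| 5 (Arm 1) | 4.9% | 14.1% | 22.6% | 41.0% |
| 10 (one later arm) | 9.6% | 26.3% | 40.1% | 65.1% |
| 35 (maximum) | 29.7% | 65.6% | 83.4% | 97.5% |

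These are chances that a carrier is present, not that a decision changes. For the decision, assume a counted event rate of 2% in non-carriers and 20% in carriers. The mixed rate is r = (1 − p) × 0.02 + p × 0.20, which is 0.029 at p = 5% and 0.038 at p = 10%.

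- Arm 1 rule (at least 1 of 5): 1 − 0.98^5 = 9.6% without carriers; 1 − 0.971^5 = 13.7% at 5%; 1 − 0.962^5 = 17.6% at 10%.
- Arms 2 to 4 rule (at least 3 of 10, binomial tail): 0.09% without carriers; 0.25% at 5%; 0.54% at 10%.
- Data Analysis rule (no pravastatin-related discontinuation), if every counted event also forces discontinuation, for n = 10: 1 − 0.98^10 = 18.3% without carriers; 1 − 0.971^10 = 25.5% at 5%.

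The three-event rule hardly moves. The effect shows in rules that a single event can trigger: the Arm 1 rule and the discontinuation condition in Data Analysis, which is not limited to Arm 1.

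**The case against.** The strongest reply is that this is a slip in one footnote and that the plan has other protection. Much of that stands.

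- **Exclusion l is not itself defective.** A reader might infer that it cannot detect chronic hepatitis B. The documents do not support that: it names no marker and accepts PCR, and the Screening section's general request could be met by testing surface antigen. The gap is in footnote 10. But no PCR is scheduled, and footnote 10 is the only text that tells a site which tests to order.
- **Attribution limits the effect.** The safety/PK algorithm counts a liver event only if it is attributed to the statin, and the Liver toxicity work-up would then reveal surface antigen as another explanation. This is partial protection. The test comes only after stopping criteria are met, and the algorithm needs a probable or definite attribution whereas the Section 5 rating table offers only related or not related.
- **The cohort rule is weak support.** Its clause on causal attribution directly follows the reference to grade 4 events. Whether it also reaches grade 3 liver events is unclear.
- **The added exposure is modest.** The TB drugs are standard care in or out of the trial. The trial adds about two weeks of pravastatin, with liver tests on Days 7, 15, 21 and 30.
- **Vaccinated people.** A reader might infer that vaccinated or immune people would be wrongly excluded. Footnote 10 specifies IgM, and nothing in the documents shows that this would happen.

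**Conclusion.** The concern holds for footnote 10. As scheduled, the screening panel does not list surface antigen, differs from the plan's own post-event list, and may miss chronic hepatitis B that exclusion l is meant to keep out. A carrier below the ALT and bilirubin limits, without cirrhosis or acute liver disease, could enter.

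The size is unknown. The presence probabilities rest on an assumed carriage rate and on every carrier passing screening, so they should not be read as chances of a wrong dose decision. The decision figures also depend on assumed event rates. They indicate only that any effect is concentrated where one event is decisive. Nor do the documents show that the sponsor chose to omit the antigen, or that a site would run the footnote literally. The correction is worth making because the text is operative and the remedy is small.

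**What to change.** Reconcile footnote 10 with the Liver toxicity list so that the screening panel names hepatitis B surface antigen as its own test. Reconcile it also with the Screening section and exclusion l by stating whether PCR is done and which of the listed results count as positive. Which results exclude is for the sponsor to state; the documents do not settle it, and no new eligibility rule is proposed here.

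The cost is one corrected footnote, a short clarification, and one routine test swapped for another on the same screening sample, with no added visit.
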